5.1. Summary of Study Design

I3Y-MC-JPCY (CYCLONE 1) is a Phase 2, open-label, single-arm, multicenter study to assess the efficacy of abemaciclib monotherapy in participants with metastatic castration-resistant prostate cancer (mCRPC) whose disease progressed on or after at least 1 androgen-axis therapy (abiraterone acetate, apalutamide, darolutamide or enzalutamide) and 2 taxane-based chemotherapy regimens (docetaxel and cabazitaxel). Participants may have received up to 3 prior systemic treatments for mCRPC, must have measurable disease per Response Evaluation Criteria in Solid Tumors version 1.1 (RECIST 1.1), and a have metastatic lesion amenable to biopsy. Androgen deprivation therapy with a gonadotropin-releasing hormone agonist must be continued throughout the study for participants who have not undergone bilateral orchiectomy. Abemaciclib 200 mg twice daily will be administered on a continuous dosing schedule until disease progression, unacceptable toxicity, or other discontinuation criteria are met.

This study will initially treat approximately 40 participants.

5.2. Determination of Sample Size

All treated patients will be included in the assessment of objective response.

An observed response rate of at least 12.5% will be considered as evidence of clinically relevant activity. Applying this rule to a 40-patient cohort yields an adequate Type I error rate and power. As an illustration of Type I error control, assuming a true response rate of 5%, the probability of observing an objective response rate (ORR) of at least 12.5% in a cohort of 40 participants is 4.8%. As an illustration of power, assuming a true response rate of 15%, the probability of observing an ORR of at least 12.5% is 73.7%.

6. A Priori Statistical Methods

6.1. General Considerations

Statistical analysis of this study will be the responsibility of Eli Lilly and Company (Lilly) or its designee. The analyses for this study will be mostly descriptive, except for possible exploratory analysis as deemed appropriate. For continuous variables, summary statistics will include the number of patients, mean, median, standard deviation, minimum, and maximum. Categorical variables will be summarized using number of patients, frequency, and percentages. Missing data will not be imputed, except for missing date of birth for analysis purpose. If birth year and month are available and date is not available or missing, date will be imputed to the 15th of that month.

The interpretation of the study results will be the responsibility of the investigator with the Lilly clinical research physician (CRP)/clinical research scientist (CRS), pharmacokineticist, and statistician. The Lilly CRP/CRS and statistician will also be responsible for the appropriate conduct of an internal review for both the final study report and any study-related material to be authorized by Lilly for publication.

Any change to the data analysis methods described in the protocol will require an amendment ONLY if it changes a principal feature of the protocol. Any other change to the data analysis methods described in the protocol, and the justification for making the change, will be described in the clinical study report (CSR). Additional exploratory analyses of the data will be conducted as deemed appropriate.

6.1.1. Populations

For the purpose of statistical analysis, following populations are defined:

Population	Description
Entered	All participants who sign the ICF
Treated/Safety	All participants who have initiated study intervention, regardless of how many doses of study intervention they receive or how many on-study research procedures are performed
Biomarker-Evaluable	All participants within the subset of participants from the treated population from whom a valid pretreatment tumor assay result has been obtained
Pharmacokinetic Analysis	All treated participants who received at least 1 dose of abemaciclib and have at least 1 evaluable PK sample

Abbreviations: ICF = informed consent form; PK = pharmacokinetics.

6.1.2. Definitions and Conventions

Study drug or study treatment refers to abemaciclib.

Date of first dose is the date of the first dose of study drug.

Study day will be calculated as

- the difference between the date of the event or assessment and the date of first dose plus 1 for all events or assessments occurring on or after the day of first dose (eg, if an event occurs on 08 January 2021 and the date of first dose was 06 January 2021, the study day of the event is 3)
- the difference between the date of the event or assessment and the date of first dose for all events or assessments occurring before the day of first dose (eg, if an event occurs on 05 January 2021 and the date of first dose was 06 January 2021, the study day of the event is -1).

One **month** is defined as 365/12 days.

Unless otherwise noted, **summaries of continuous variables** will include a mean, median, standard deviation, minimum, and maximum.

Unless otherwise noted, **summaries of categorical variables** will include the frequency and percentage (relative to the population being analyzed) of each category.

The assumptions for each statistical method will be evaluated. If there is violation of assumptions, alternative statistical methods may be used. Additional exploratory analyses of the data will be conducted as deemed appropriate. Unless otherwise stated, all tests of treatment effects will be conducted at a 1-sided alpha level of .025, and all confidence intervals (CIs) will be given at a 2-sided 95% level.

6.2. Handling of Dropouts or Missing Data

With the exception of dates, missing data will not be imputed. The method of imputation for any dates that are imputed is described in the relevant section.

6.3. Patient Disposition

A detailed description of patient disposition will be provided. It will include a summary of the number and percentage of patients entered into the study, treated in the study, reasons for discontinuation from study treatment, and reasons for discontinuation from study. Reason for discontinuation from both study treatment and the study will be summarized by predetermined categories. If the reason for discontinuation is an adverse event (AE), the associated AE term will be reported.

6.4. Patient/Subject Characteristics

6.4.1. Demographics

Patient demographics will be summarized for all treated patients. Patient demographics will include sex, race, ethnicity, country, age, height, weight, and body mass index.

6.4.2. Baseline Disease Characteristics

Disease characteristics will be summarized. Disease characteristics will include the following:

- initial pathological diagnosis

- disease stage - TNM stage, Gleason score and prostate-specific antigen (PSA) at initial diagnosis
- time from initial diagnosis to:
 - castration-resistant prostate cancer (CRPC)
 - study treatment start date
- PSA doubling time prior to study treatment
- type of progression at study entry (PSA progression and/or radiographic progression)
- nature of disease (bone/nodal disease only, visceral metastases, or other)
- number of organs involved (1, 2, or 3 or more)
- metastatic site(s)
- baseline Eastern Cooperative Oncology Group (ECOG) Performance Status (PS), and
- baseline laboratory values (PSA, testosterone, lactate dehydrogenase [LDH], alkaline phosphatase [ALP], hemoglobin [Hb], albumin).

Disease stage (I-IV) at initial diagnosis will be derived based on TNM stage, Gleason score, and PSA.

Nature of disease and number of organs involved will be derived from the baseline electronic clinical (case) report forms: 'Target Tumor: RECIST 1.1 (Tumor Assessment)' and 'Non-Target Tumor: RECIST 1.1 (Tumor Assessment)' for soft tissue, and 'Bone Lesion – Baseline (Tumor Assessment)'. The number of organs involved in soft tissue will be derived from the location codes of the target and non-target lesions.

6.4.3. *Historical Illnesses*

Historical illnesses are clinically relevant events in the past that ended before the screening visit. Historical illnesses (using Preferred Terms [PTs] from the most current version of the Medical Dictionary for Regulatory Activities [MedDRA]) will be summarized.

6.4.4. *Prior Therapies*

Prior radiotherapy, surgery, and systemic therapy will be summarized. Prior radiotherapy and surgery will be categorized by reason for regimen. Prior systemic therapies will be categorized by type of regimen (endocrine therapy, chemotherapy, targeted therapy, or other) and reason for regimen ([neo]adjuvant therapy or therapy for locally advanced, nonmetastatic castration-resistant, metastatic hormone-sensitive, or metastatic castration-resistant disease). Frequency of each specific therapy will be tabulated within each type of regimen and reason for regimen.

6.4.5. *Therapies After Study Treatment Discontinuation*

The numbers and percentages of participants receiving anticancer therapies after study treatment discontinuation will be provided by type of therapy (surgery, radiotherapy, or systemic therapy) and by drug class and/or name, overall and by line of therapy.

Systemic therapies received following study treatment discontinuation will be summarized.

Therapies will be summarized overall and by category:

- endocrine therapy
- chemotherapy
- targeted therapy, or
- other.

6.5. *Treatment Compliance*

Treatment compliance for abemaciclib will be measured by pill counts and summarized cumulatively. Compliance will be calculated as the ratio of total dose taken to the total assigned dose (plus or minus any dose adjustments and doses omitted/withheld). The total assigned dose for a patient with no adjustments or omissions is as follows:

- 200 mg per dose \times 2 doses per day \times number of days on study drug

6.6. *Concomitant Therapy*

All medications will be coded to the generic preferred name according to the current World Health Organization (WHO) drug dictionary. All concomitant medications will be summarized by number and percentage of patients for the treated population using the base name (without esters or salts).

6.7. *Efficacy Analyses*

Unless otherwise noted, all efficacy analyses will be performed on the treated population. Patients with a nonevaluable or unknown response per each specified criteria will be considered nonresponders for the purpose of calculating response rates.

Unless otherwise stated, all tests of treatment effects will be conducted at a 1-sided alpha level of .025, and all CIs will be given at a 2-sided 95% level.

Objective response rate is the primary endpoint for this study. The study will be considered positive if ORR is positive at its primary analysis, as described below.

6.7.1. *Primary Outcome and Methodology*

The primary endpoint for this study is ORR, defined as the proportion of participants who have a soft tissue best overall response (BOR) of complete response (CR) or partial response (PR) per RECIST 1.1 and do not have concurrent bone disease progression per Prostate Cancer Working Group 3 (PCWG3) criteria, as assessed by the investigator/local radiologist. The primary analysis will require confirmation of responses, but, when appropriate, response rates including

both confirmed and unconfirmed responses may also be reported. Calculation of BOR will be done for each patient in the treated population and will include all response evaluations through the short-term follow-up visit and before the initiation of poststudy-treatment discontinuation therapy.

The primary analysis of the primary endpoint of ORR will be performed approximately 6 months after the last patient enters treatment. In certain circumstances, it may be appropriate to perform the primary analysis earlier (for instance, if all treated patients have experienced objective disease progression). All secondary endpoints will be evaluated at this time. Additional updated analyses of efficacy and safety may be conducted at later times if deemed appropriate by the sponsor.

The ORR will be evaluated against a null hypothesis of 5%. At the time of primary analysis, if 5 or more responders are observed in the planned 40 patients, the study will be considered positive. This is equivalent to a p-value $<.05$ for the exact test of a null hypothesis of an ORR of 5% against an alternative of ORR $>5\%$.

Lilly or its designee will collect and store tumor assessment images, and an independent review of imaging scans may be performed by Lilly or its designee. Analyses of ORR may be repeated using independently reviewed BOR and presented as sensitivity analyses.

6.7.2. Secondary Efficacy Analyses

6.7.2.1. Radiographic Progression-Free Survival

The radiographic progression-free survival (rPFS) time is measured from the date of first dose to the earliest date of investigator-determined radiographic disease progression (by objective radiographic disease assessment per RECIST 1.1 for soft tissue AND/OR radionuclide bone scan using PCWG3 criteria for bone) or death from any cause, whichever occurs first. Patients who have neither progressed nor died will be censored at the day of their last radiographic tumor assessment (if available) or date of first dose if no postinitiation (ie, postbaseline) radiographic assessment is available. The detailed censoring rules are described in [Table JPCY.6.1](#).

Radiographic progression-free survival will be summarized and listed for all treated patients. The Kaplan-Meier (KM) method (Kaplan and Meier 1958) will be used to estimate the rPFS curve as well as rPFS rates at 3, 6, 9, and 12 months.

Table JPCY.6.1. rPFS Event/Censoring Scheme

Situation ^a	Event/Censor	Date of Event or Censor
Radiographic disease progression or death	Event	Earliest date of radiographic disease progression or death ^b
No radiographic disease progression and no death	Censored	Date of last adequate radiographic assessment showing no evidence of disease progression or date of first dose (whichever is later) ^c
Unless		
No baseline radiographic tumor assessment available	Censored	Date of first dose
No adequate postbaseline radiographic tumor assessment available and death reported after 2 scan intervals following first dose ^{c,d}	Censored	Date of first dose
New anticancer treatment started and no radiographic disease progression or death within 14 days	Censored	Date of last adequate radiographic assessment showing no evidence of disease progression prior to (start of new therapy +14 days) or date of first dose (whichever is later) ^c
Radiographic disease progression or death documented after 2 or more scan intervals following last adequate radiographic tumor assessment or first dose (whichever is later) ^{c,d}	Censored	Date of last adequate radiographic assessment showing no evidence of disease progression or date of first dose (whichever is later) ^c

Abbreviations: CR = complete response; PD = progressive disease; PR = partial response; rPFS = radiographic progression-free survival; SD = stable disease.

- a Clinical/symptomatic deterioration that is not radiologically confirmed will not be considered as radiographic disease progression.
- b To be specific, once the radiographic disease progression is observed, especially for confirmed bone progression, the date of disease progression is the date at which initial bone progression (or soft tissue progression, whichever is earlier) is observed, not the date that the bone progression is confirmed by a subsequent assessment.
- c Adequate radiographic tumor assessment refers to an assessment of one of the following:
 - Soft tissue disease with one of the following responses: CR, PR, SD; and adequate bone scan showing no or initial evidence of disease progression.
 - Soft tissue disease with a response of PD.
 - Bone scan showing confirmed disease progression.
 To be specific, “last adequate radiographic assessment showing no evidence of disease progression,” does not include the assessment showing initial/unconfirmed evidence of bone progression. If tumor scans for 1 assessment were performed on multiple days, use the earliest scan date for that visit as the date of assessment.
- d Two scan intervals refer to the time period of next 2 protocol-scheduled radiographic tumor assessments. Time is measured from the last adequate radiographic tumor assessment date. The window of the tumor assessment is also considered. For example, if the last adequate assessment occurs during Cycle 3, the next 2 protocol-mandated assessments are Cycle 5 and Cycle 7, and the window around each assessment is 7 days, then 2 scan intervals will be considered as $2*(28*2 + 7) = 126$ days.

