## 7. Discontinuation of Study Intervention and Participant Discontinuation/Withdrawal

### 7.1. Discontinuation of Study Intervention

Participants may discontinue the study intervention at any time for any reason. Investigators should try to find out the reason and document it on the corresponding CRF.

The reason and date of discontinuation will be collected for all participants.

Participants with PSA-only progression should continue study intervention until disease progression (radiographic and/or symptomatic progression), when participant safety is not compromised.

Study intervention should be continued for as long as the participant consents and complies with study procedures and requirements, is tolerating the study intervention, until radiographic progression according to RECIST 1.1 for soft tissue and/or PCWG3 for bone; and/or until symptomatic progression.

Symptomatic progression is defined as:

- Symptomatic Skeletal Event (SSE), defined as symptomatic fracture, surgery or radiation to bone, or spinal cord compression
- Pain progression or worsening of disease-related symptoms requiring initiation of a new systemic anti-cancer therapy.
- Development of clinically significant symptoms due to loco-regional tumor progression requiring surgical intervention or radiation therapy.

When study intervention is discontinued due to symptomatic progression, the investigator should obtain CT/MRI and bone scan imaging within 14 days to assess for radiographic progression, prior to the participant initiating radiotherapy, surgery or subsequent anti-cancer therapy (whichever comes first).

Patients discontinuing study intervention due to documented radiographic progression will be followed for the development of symptomatic progression until start of new anticancer therapy, withdrawal of consent, death, or study completion, whichever occurs first.

Participants discontinuing study intervention prior to documented radiographic progression will continue to have scheduled disease assessments until documented radiographic progression, start of new anticancer therapy, withdrawal of consent, death, or study completion, whichever occurs first.

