### **Bone Progression per PCWG3**

A participant is considered to have progressed by bone scan if:

1. For radiographic disease progression on bone observed on the first post-treatment bone scan
  - Appearance of at least 2 new lesions on the first post-treatment scan (Week 9), with at least 2 additional lesions on the next scan (Week 17; 2+2 rule).
  - The date of progression is the date of the first post-treatment scan, when the first 2 new lesions were documented.

OR

2. For radiographic disease progression in bone observed after the first post-treatment bone scan (Week 17 or later):
  - Appearance of at least 2 new lesions relative to the first post-treatment scan (Week 9, new baseline) that are persisting on a confirmatory subsequent scan (at least 6 weeks later or at the next scheduled assessment).
  - The date of progression is the date of the scan that first documents the second lesion.

Changes in intensity of uptake alone do not constitute either progression or regression.

Date Progression Detected	Criteria for Progression	Criteria for Confirmation or Progression (Requirement and Timing)	Criteria for Documentation of Disease Progression on Subsequent Scan
Week 9 (C3D1) (or earlier unscheduled visit)	Two or more new lesions compared to baseline bone scan	Requires confirmation at least 6 weeks after progression identified or at the Week 17 assessment	Confirmatory scan: Two or more new bone lesions compared to Week 9 scan
Week 17 or later	Two or more new lesions on bone scan compared to Week 9 bone scan	Requires confirmation at least 6 weeks after progression identified or at the next scheduled assessment	Confirmatory scan: Two or more persisting (i.e., also present on the prior scan) new lesions relative to Week 9 scan

Abbreviations: C = cycle; D = day.

Source: Scher et al. 2016.

**Overall Survival** is defined as the time from the date of treatment initiation to date of death due to any cause. For participants not known to have died at the time of analysis, OS will be censored at the last known alive date.

**Duration of Response** is defined as the time from first documented evidence of soft tissue CR or PR until earliest date of disease progression by objective radiographic disease assessment per RECIST 1.1 for soft tissue AND/OR radionuclide bone scan using PCWG3 criteria for bone as assessed by the investigator/local radiologist, or death from any cause, whichever occurs first.

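### Bone lesions followed by new therapy before confirmation are censored for rPFS rather than counted, and no planned analysis tests this informative censoring

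*SAP*

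**What the plan says.** **When bone lesions count.** Protocol 8.1.1 (Bone Progression per PCWG3) accepts bone progression only when confirmed. For lesions on the first post-treatment scan the rule is "Appearance of at least 2 new lesions on the first post-treatment scan (Week 9), with at least 2 additional lesions on the next scan", and the accompanying table says "Requires confirmation at least 6 weeks after progression identified or at the Week 17 assessment". Lesions first seen at Week 17 or later must persist on a further scan. Soft-tissue progression needs no confirmation.

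**When imaging stops.** Under Protocol 7.1, patients who stop abemaciclib before radiographic progression "will continue to have scheduled disease assessments until documented radiographic progression, start of new anticancer therapy", among other end points. If treatment stops for symptomatic progression, "the investigator should obtain CT/MRI and bone scan imaging within 14 days to assess for radiographic progression", before the next treatment begins.

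**How the patient is scored.** One row of SAP Table JPCY.6.1 censors on this situation: "New anticancer treatment started and no radiographic disease progression or death within 14 days". The censoring date is "Date of last adequate radiographic assessment showing no evidence of disease progression prior to (start of new therapy +14 days) or date of first dose"; the later of the two applies. Footnote c then says that the last clean scan "does not include the assessment showing initial/unconfirmed evidence of bone progression". If the same lesions are later confirmed, footnote b makes the patient an event, and "the date of disease progression is the date at which initial bone progression (or soft tissue progression, whichever is earlier) is observed".

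**Related text.** The body of SAP 6.7.2.1 censors at the last radiographic assessment and does not mention this exclusion. SAP 6.7.2.3 applies the rPFS censoring rules to DoR. Protocol 9.4.3 leaves sensitivity analyses for time-to-event endpoints to the SAP. SAP 6.7.3 lists only blinded independent review, as appropriate.

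**The concern.** Whether a patient with new bone lesions becomes an event can depend on when he changes therapy. If he waits for a confirming scan, he is an event at the lesion scan. If he switches first, he is censored at the scan before the lesions, or at first dose when they appear at Week 9. A death more than 14 days after the switch is not counted either.

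The protocol itself opens this path. Symptomatic progression includes worsening that needs new systemic therapy, and it triggers a bone scan just before that therapy. Lesions first seen on that scan are unconfirmed when the patient switches. The patients removed are therefore likely to be doing worse than those who remain, whereas Kaplan-Meier assumes that censored patients share the future risk of the rest.

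At stake are the rPFS curve, its median and its 3-, 6-, 9- and 12-month rates, and DoR. The trial has a single arm, so no comparator shares the bias.

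**Working it through.** **1. The plan's own figures.** The documents give no rPFS assumption, event count or power. Their design figures are for ORR. With 40 patients and success at 5 or more responders, the exact binomial gives 4.80% at a true rate of 5% and 73.7% at 15%, matching the stated 4.8% and 73.7%. The two-scan-interval figure also reproduces: 2 × (28 × 2 + 7) = 126 days.

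**2. Hand example at the first scan.** Take 40 patients, 16 of whom progress, and let *c* of the 16 have unconfirmed bone lesions and new therapy.

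- All counted as events: 1 − 16/40 = 60.0%.
- SAP rule (the *c* patients leave at day 1): with c = 4, 1 − 12/36 = 66.7%; with c = 8, 1 − 8/32 = 75.0%.
- Same patients censored at the lesion scan instead: 1 − 12/40 = 70.0%; 1 − 8/40 = 80.0%.

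The rise comes from the uncounted event. Footnote c's earlier date makes the rise smaller.

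**3. Six-month rate.** Inputs:

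- Scans every 56 days (Protocol 1.3), so three scans fall within 6 months (182.5 days).
- Exponential rPFS with a median of 3.7 months. This is borrowed from the anti-androgen arm of the cabazitaxel trial described in Protocol 4.2 and is not a design assumption here. Medians of 2.5 and 6.0 months were also tried.
- *q*, the share of progressions that are bone-only, unconfirmed and followed by new therapy. It is assumed, because the documents do not give it. All such cases are taken as real progression.

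With a month of 365/12 days, the chance of passing one scan interval is S = 2^(−56/(3.7 × 30.42)) = 0.708, so p = 1 − S = 0.292. The Kaplan-Meier factor per scan is:

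- counted as events: S
- SAP rule: 1 − (1 − q)p/(1 − qp) = S/(1 − qp)
- censored at the lesion scan: 1 − (1 − q)p

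Cubing each gives the 6-month rate:

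| q | Counted as events | SAP rule | Rise (points) | Censored at lesion scan |
|---|---|---|---|---|
| 10% | 35.5% | 38.8% | 3.3 | 40.1% |
| 20% | 35.5% | 42.6% | 7.0 | 45.1% |
| 30% | 35.5% | 46.8% | 11.2 | 50.4% |

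The same formulas for q = 10%, 20% and 30% give 21.6% rising to 24.4%, 27.8% and 31.7% with a 2.5-month median, and 52.8% rising to 56.0%, 59.4% and 63.1% with a 6.0-month median. Simulated samples of 40 patients (median 3.7 months) gave mean rises of 3.3, 7.0 and 11.2 points.

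**4. If the lesions are flare.** In the hand example, let all 16 progressions be counted and let 4 of the 24 non-progressors be flare cases who switch therapy. Removing them at day 1 gives 1 − 16/36 = 55.6% against 60.0%. With the 3.7-month median, censoring at day 1 a share r of those progression-free at Week 9 gives [1 − p/(1 − rS)] × S². This is 34.4% for r = 10% and 33.1% for r = 20%, against 35.5%.

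**The case against.** **The affected group is narrow.** Every participant has measurable disease, and soft-tissue progression on the same scan is an event without confirmation. Patients are meant to stay on treatment until confirmed bone, soft-tissue or symptomatic progression. For a Week 9 finding, a pre-therapy scan from about Week 15 (9 + 6) can already confirm it, so a reader should not assume that every switch before Week 17 is lost. All of this stands, and it limits numbers without removing the path.

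**The shares have no source.** In the cabazitaxel trial cited in Protocol 4.2, 53.5% of the cabazitaxel group received any later anticancer treatment. Taken as a rough guide only (an earlier line, and patients rather than progressions), a 30% share would need 30/53.5 = 56% of such patients to follow this exact path, and 20% would need 37%. The upper end of the range is therefore demanding.

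**A reader might infer that footnote c's back-dating causes the inflation.** Steps 2 and 3 show the opposite. Deleting that sentence while keeping the non-event would raise the estimate further.

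**A reader might also infer that the rule always favours the drug.** Step 4 shows that it does not. Lesions that would not have been confirmed are not progression under the 2+2 rule, and censoring those patients early lowers the estimate. The net direction depends on the flare share, which the documents do not give.

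**Other endpoints catch some of the decline.** Worsening that needs new systemic therapy is an event in time to symptomatic progression, OS is followed after new therapy, and rPFS is listed by patient. This helps interpretation but does not correct the rPFS curve.

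**Conclusion.** The concern holds in a limited form. The rules turn unconfirmed bone-only progression followed by new therapy into a censored observation, and that censoring is informative. The resulting bias is upward to the extent that the lesions are true progression.

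The size is conditional. About 3, 7 or 11 points on the 6-month rate at shares of 10%, 20% or 30% rests on an assumed share, exponential rPFS, a borrowed median and every case being real. The median may also move to a later scan, but much of that reflects the 56-day scan grid, so no weight is put on it here.

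The documents do not support reading this as a threat to the trial's conclusion. rPFS is secondary and descriptive, and the success rule of 5 or more responders in 40 is untouched. DoR does inherit the rules, and blinded independent review changes who reads the scans without specifying a different censoring rule. The plan should address this, but it is not a critical flaw.

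**What to change.** - **Sensitivity analysis.** Add to SAP 6.7.3 a prespecified analysis of rPFS and DoR that counts initial bone progression (two or more new lesions) as an event on its first date when new anticancer therapy starts before confirmation. Leave the main rule as it is.
- **Scope.** Do not apply it to patients who are merely awaiting a confirming scan at data cut-off. A trigger based only on the absence of a further bone scan would wrongly turn them into events.
- **Reporting.** Give the number of patients who take this path. If there are few, this supports the robustness of rPFS to the rule.
- **Wording.** Reconcile the body text of SAP 6.7.2.1 (last radiographic assessment) with footnote c of Table JPCY.6.1 (last clean scan), since they can give different censoring dates.

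The cost is a few lines of SAP text and one extra analysis of each endpoint, using scan and therapy dates that the protocol already collects. The small downside is that some flare may be counted as progression, in the sensitivity run only.
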